### **Hypothesis 1: Outcome Variables Main Effects for Community Re-integration Factors**

This algorithm is based on the assumption that an interaction between the intervention group and control groups can be modeled as a fixed effect. An LMM will then be used to evaluate whether the intervention had an effect at any time point or whether the intervention influenced change (growth, trajectory) in the outcome over the course of the study. The following will be considered for the analytical strategy:

- ANOVA, Repeated-measures ANOVA as well as MANCOVA will be used to compare the effect of the COMPASSgoal intervention vs. supported discharge group determined via baseline assessment. ANOVA will be used to compare the change from pre- to post-intervention between the two groups. Furthermore, in order to analyze the main effect of the COMPASSgoal intervention over time, a two-way repeated measures parametric ANOVA, as well as a non-parametric repeated measures Friedman ANOVA, will be performed, using the baseline time point, levels of TBI self-efficacy, or real-world tasks performance as the dependent variables. The levels of the repeated measures factor correspond to the number of assessments: baseline (pre-intervention) and 2 months post-intervention. The between-groups factor will be the intervention group vs. the supported discharge group. MANCOVA analysis will focus on the contrast in TBI self-efficacy between the intervention and supported discharge groups while accounting for a specified covariate: level of executive impairment as defined by FrSBE. In the case of non-normal residuals, we will use a nonparametric repeated measures approach. In the case of missing data, an LMM, which uses a maximum likelihood estimate to correct for unequal number of measures per subject, will be employed.
- *We will use Linear mixed models to control for potential confounding variables and baseline values will be utilized as a covariate. These models will allow for the additional control of potential within subjects clusters. These clusters, though not part of the formal hypothesis testing but byproducts of these models, will allow for conceptualization of additional future hypotheses.*

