### **Power and sample size calculation**

110 participants with executive dysfunction due to diagnosed TBI will be randomized into the COMPASSgoal intervention or supported discharge groups, as assessed via the VHA TBI Comprehensive Evaluation screening tool. Participants in the supported discharge group will not receive the intervention, but will receive usual care provided by case managers with increased intensity of communication prompts. Participants in the intervention group will receive 8 goal self-management sessions over a period of approximately 10 weeks. We don't expect a significant change from post-intervention to 3 month post-intervention, the sample size calculations are based on a t-test for comparisons of mean change in the Community Reintegration of Service members (CRIS) subscale from pre- to post-intervention between two groups.

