### **Hypothesis:**

H0:  $\mu_1 = \mu_2$  where  $\mu_1$ = mean change in CRIS subscale from time 1 to time 2 in self-management group and  $\mu_2$ = mean change in CRIS subscale from time 1 to time 2 in supported discharge group  
H1:  $\mu_1 \neq \mu_2$

**Power Calculation:** PASS (Power Analysis and Sample Size Software, Kaysville, UT, 2008) was used for the power calculation. The primary outcome of this study is the frequency of social interactions measured via the Extent of Participation subscale of the CRIS. The power calculation was performed based on the hypothesis listed above by using a two-sided t-test with assumption of normality. The level of significance was set at 0.05 and power was set at 90%. The effect size and standard deviation used for the power calculation were estimated based on a previous VA study and clinical judgment. 44 subjects in each

[figure not shown]
group, for a total of 88 subjects will provide 90% power to test an effect size of 0.71 with a SD of 7 for difference in CRIS subscale score between groups with  $\alpha=0.05$  (two sided). After adjustment for 20% loss to follow-up, we will recruit 55 subjects in each group of this study, a total of 110 subjects.

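### Hypothesis 1 has several overlapping analyses and no named primary, and because the promised Bonferroni family is undefined, the sized two-sided 0.05 with 90% power is not tied to one test

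*Combined protocol and SAP*

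**What the plan says.** The sample size sections define one test. Under Power and sample size calculation, "the sample size calculations are based on a t-test for comparisons of mean change" in a CRIS subscale from before to after the intervention. The power paragraph identifies the subscale as Extent of Participation and says the calculation was made "by using a two-sided t-test with assumption of normality". It adds: "The level of significance was set at 0.05 and power was set at 90" per cent.

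The SAP section on Hypothesis 1 is wider:

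- It opens with the LMM: "An LMM will then be used to evaluate whether the intervention had an effect at any time point or whether the intervention influenced change" over the study.
- Then "ANOVA, Repeated-measures ANOVA as well as MANCOVA will be used to compare the effect of the COMPASS" intervention with supported discharge.
- "ANOVA will be used to compare the change from pre- to post-intervention between the two groups". This is the sized test.
- A two-way repeated-measures ANOVA and a Friedman ANOVA follow. Self-efficacy and real-world task performance are among their dependent variables; CRIS is not named.
- The MANCOVA is on TBI self-efficacy, with FrSBe as covariate.
- One switch depends on the residuals: "In the case of non-normal residuals, we will use a nonparametric repeated measures approach".
- A second switch depends on incomplete follow-up and moves the analysis to a mixed model: "In the case of missing data, an LMM, which uses a maximum likelihood estimate to correct for unequal number of measures per subject".
- A second bullet adds LMMs with the baseline value as covariate.

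The SAP Overview calls ANOVA and repeated-measures ANOVA the basic tests and promises Bonferroni adjustment, with no family, number of tests or divided alpha. It describes the primary outcome as change in three types of parameters, not one subscale. The Missing Data section adds complete-case analysis if data are judged missing completely at random.

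**The concern.** If the listed analyses disagree, no sentence says which one decides Hypothesis 1. A two-sided 0.05 is the error rate of one test fixed in advance. It is not the error rate of a procedure that may succeed on the change score, on the adjusted comparison, at either later visit, or on the trajectory.

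The Bonferroni sentence could contain this, but its scope is open and each reading has a cost. If it does not cover alternative models and visits, the type I error is above 5%. If it does, the power calculation no longer applies, because it used the full 0.05. Either way, the stated pairing of 0.05 with 90% power does not describe the analysis as written.

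**Working it through.** **Inputs.** From the power paragraph: effect size 0.71, SD 7, two-sided alpha 0.05, 90% power, 44 per arm, 20% loss, 55 per arm recruited. The correlation r between visits is not given; I assume 0.3 to 0.8. The simulations use complete data and approximate the LMM contrasts by a baseline-adjusted ANCOVA at each visit. T2 is post-intervention and T3 the 3-month follow-up.

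**1. The plan's figure.** Normal approximation: n = 2(1.960 + 1.282)²/0.71² = 41.7, so 42 per arm. The exact t calculation gives 42.7, so 43. At 44 per arm the power is 0.909, and 44/0.8 = 55. The figure is reproduced. The 0.71 must be standardised (about 5/7): as raw points with SD 7 it would need 2,043 per arm.

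**2. How many distinct tests.** With two time levels, the repeated-measures group-by-time F equals the square of the change-score t. In a worked example both are 0.4352 with p = 0.511, so these are one test. The repeated-measures group main effect is a different test. Friedman compares visits within subjects and does not by itself compare arms.

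**3. No adjustment, any significant result counts** (simulated null, 44 per arm):

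| Set of tests, each at 0.05 | False positives |
|---|---|
| Change score alone | 4.8–5.1% |
| Change score or baseline-adjusted, T2 | 6.3–7.6% |
| The same plus a rank test | 7.1–8.5% |
| Baseline-adjusted, T2 or T3 | 9.0–9.5% |
| T2 set above plus FrSBe-adjusted test and repeated-measures main effect | 12.6–13.1% |
| Five tests: change, rank and adjusted at T2; change and adjusted at T3 | 12.8–16.0% |
| Widest set examined | 17.9–19.2% |

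Two exact 5% tests cannot together exceed 2 × 0.05 = 10%, which caps the T2-or-T3 row.

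**4. Bonferroni over five tests** (alpha 0.05/5 = 0.01). False positives fall to 2.6–3.6% for the five-test set and 4.1–4.6% for the widest set. For the sized test at 44 per arm the noncentrality is 0.71 × √(44/2) = 3.33. Power is 0.909 at alpha 0.05 and 0.755 at 0.01. Recovering 90% needs 61 evaluable per arm; 61/0.8 = 76.25, so 77 recruited instead of 55.

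**5. The residual switch alone.** Shapiro test on the residuals, then t or rank test: 4.6–5.8%.

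**6. Change score against baseline adjustment.** With equal variances at the two visits, change has variance 2σ²(1 − r) and the baseline-adjusted outcome σ²(1 − r²). The ratio is (1 + r)/2, so the standardised effect becomes 0.71/√((1 + r)/2).

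| r | Variance ratio | Power at 44 per arm | n per arm for 90% |
|---|---|---|---|
| 0.3 | 0.65 | 0.983 | 29 |
| 0.5 | 0.75 | 0.967 | 33 |
| 0.7 | 0.85 | 0.946 | 37 |
| 0.8 | 0.90 | 0.935 | 39 |

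**The case against.** The strongest reply is that the sample size section already implies a primary test. It gives the hypotheses, outcome, two visits, sidedness and alpha, and the change ANOVA in the SAP is that test. This is a fair inference, but the SAP does not state it, and its Overview defines the primary outcome more broadly.

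The second reply is the Bonferroni sentence. It stands in part: applied to the listed tests, it keeps the error below 5%. A reader might therefore infer too much from the 13 to 19% figures. They hold only with unadjusted tests and any win counted, which the documents neither adopt nor exclude.

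Three other strong readings are not supported:

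- **Five or more competing tests of one arm effect on one outcome.** The MANCOVA is on self-efficacy, Friedman alone does not compare arms, and the two-level interaction duplicates the change test.
- **Residual-based switching as a source of inflation.** It stays near 5%. Nor does the text show that the switch discards covariates: baseline is a level of the repeated factor, and FrSBe is attached only to the MANCOVA.
- **An underpowered change-score test.** It has 0.909 power on the plan's own inputs; baseline adjustment is a gain in precision.

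It can also be said that with 20% expected loss the missing-data rule leads predictably to an LMM, so little choice is left. That is largely right about the model class. It does not settle which LMM contrast decides, and the Missing Data section still offers complete-case analysis.

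**Conclusion.** The concern holds in this form: several overlapping analyses, two data-dependent switches and an open-ended LMM criterion, with no analysis named primary and a Bonferroni rule without a family. The consequence depends on how that rule is read. Outside its cover, false positives are about 9 to 10% for T2 or T3 alone and about 13 to 19% for wider sets. With five tests under it, power is about 0.755 instead of 0.909. The error rates and the precision gain rest on assumed visit correlations and complete data; the loss of power at alpha 0.01 rests only on the plan's own inputs. The sample size itself is sound for one test at 0.05. The deciding test should be fixed before outcome data are analysed.

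**What to change.** In the SAP section on Hypothesis 1, name one primary analysis: an LMM of CRIS Extent of Participation with T2 and T3 as responses, and arm, visit, arm-by-visit, baseline CRIS and baseline FrSBe as fixed effects. Baseline should not also be a response. The two-sided 0.05 decision rests on the arm contrast at T2.

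Make T3, trajectory and TBI self-efficacy secondary. Since Study Hypothesis 1 names self-efficacy alongside community integration, say there that it is tested as a secondary outcome. Keep the change-score ANOVA and a rank-based comparison of arms as sensitivity analyses that never replace the primary.

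Delete the residual and missing-data switches and the any-visit criterion, and align the Missing Data section, so that the LMM is used whatever the missingness.

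In the SAP Overview, replace the three-parameter primary outcome with the single subscale in the power paragraph. State that Bonferroni applies to the named secondary outcomes and not to the single primary test.

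The cost is wording: the model is already listed and no further data are needed. The sponsor gives up choosing the test afterwards.

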### Study Hypotheses:

[figure not shown]
Study Hypothesis 1: Participants in the COMPASSgoal group will have higher TBI self-efficacy and higher community integration scores over time than participants in the supported discharge group matched on executive dysfunction score;

Study Hypothesis 2: *Individual psychosocial profile (emotional status, resilience, and level of post-traumatic stress disorder, PTSD) will mediate the responsiveness to the COMPASSgoal intervention, measured through the standardized experimental performance of everyday tasks, in Veterans with impaired executive function due to TBI.*

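### The Friedman ANOVA named for Hypothesis 1 has no between-group term, so it cannot compare COMPASS with supported discharge, whether run pooled or within each arm.

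*Combined protocol and SAP*

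**What the plan says.** The protocol's Study Hypotheses section makes Hypothesis 1 a comparison between arms: the COMPASS "group will have higher TBI self-efficacy and higher community integration scores over time than participants in the supported discharge group".

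The SAP section for Hypothesis 1 opens its list of methods with "The following will be considered for the analytical strategy". Within that list, for the effect of COMPASS over time, it commits to "a two-way repeated measures parametric ANOVA, as well as a non-parametric repeated measures Friedman ANOVA, will be performed". The outcomes for that analysis are then listed: "using the baseline time point, levels of TBI self-efficacy, or real-world tasks performance as the dependent variables". The design for the same sentence is fixed next:

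- Repeated factor: "The levels of the repeated measures factor correspond to the number of assessments: baseline (pre-intervention) and 2 months post-intervention".
- Group factor: "The between-groups factor will be the intervention group vs. the supported discharge group".

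The same paragraph adds a conditional rule: "In the case of non-normal residuals, we will use a nonparametric repeated measures approach". No method is named there. Friedman is the only nonparametric method the plan names.

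The section also plans analyses that do compare the arms. One is "ANOVA will be used to compare the change from pre- to post-intervention between the two groups"; the others are a MANCOVA contrast in TBI self-efficacy and linear mixed models. The SAP Overview names ANOVA and repeated measures ANOVA as the basic tests and promises Bonferroni adjustment.

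**The concern.** Friedman's test ranks each participant's own values across the repeated assessments and asks whether those ranks differ systematically by assessment. It is a one-factor test of time. Declaring a between-groups factor does not add one to the statistic.

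The plan does not say whether the test would be run on both arms pooled or within each arm. Neither version answers Hypothesis 1:

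- **Pooled**, it ignores arm. A significant result shows that participants changed, not that COMPASS changed them more.
- **Within each arm**, it gives two separate tests of time and no contrast. Finding COMPASS significant and control not significant is not evidence of a difference between them.

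The risk is that change shared by both arms gets reported as an effect of the intervention. The documents are mixed on how much shared change to expect. The ICF section aims to document natural recovery, and the Supported Discharge section says control contacts prompt reflection, although on community integration rather than on the outcomes in the Friedman sentence. The rationale for the recruitment assessment, however, describes injuries months or years old, which suggests that shared change may be small.

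**Working it through.** **Inputs.** From Power and sample size calculation: 44 completers per arm, 55 recruited per arm, effect size 0.71 (read as a standardised difference), two-sided alpha 0.05, 90% power, 20% loss. From SAP Hypothesis 1: two assessments, two arms. Assumed, because the documents give no expected control-arm change: both arms shift by 0.1, 0.2, 0.3 or 0.5 SD of change, with normal change scores, equal variances and no ties.

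**1. The plan's own sample size.** The noncentral t calculation at d = 0.71 needs 42.7, so 43 per arm. At 44 per arm the noncentrality is 0.71 × √(44/2) = 3.33 on 86 df, giving power 0.909. Then 44/(1 − 0.20) = 55 per arm, 110 in total. The stated size reproduces, and the present point does not depend on it.

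**2. What Friedman becomes with two assessments.** With n₊ participants improving, n₋ worsening and n = n₊ + n₋, the statistic is

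Q = (n₊ − n₋)² / n, compared with chi-square on 1 df (critical value 3.84).

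This is the sign test on change. Arm does not appear in it. In a simulated data set of 88, shuffling the participants across arms left the pooled p-value at 0.1356.

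**3. Both arms improve equally, no treatment effect.** Each participant improves with probability p = Φ(shift). Pooled, n = 88, Q exceeds 3.84 when n₊ ≥ 54 or n₊ ≤ 34. By arm, n = 44, it does so when n₊ ≥ 29 or n₊ ≤ 15. Exact binomial probabilities follow, with r the by-arm rejection rate and r(1 − r) the chance that COMPASS is significant and control is not:

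| Shared shift (SD) | p | Pooled rejects | By-arm r | COMPASS only, r(1 − r) |
|---|---|---|---|---|
| 0 | 0.500 | 0.042 | 0.049 | 0.046 |
| 0.1 | 0.540 | 0.102 | 0.081 | 0.074 |
| 0.2 | 0.579 | 0.295 | 0.180 | 0.148 |
| 0.3 | 0.618 | 0.579 | 0.346 | 0.226 |
| 0.5 | 0.691 | 0.953 | 0.739 | 0.193 |

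A rank-sum test on change rejects in 0.048 to 0.050 of trials across these shifts (simulation, 20,000 trials each).

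**4. A real treatment effect.** Suppose control does not change (p = 0.5) and COMPASS improves by 0.71 SD (p = Φ(0.71) = 0.761). Convolving the two binomials of 44 gives pooled Friedman power of 0.678. Rank-sum on change has 0.893 (200,000 trials) and the t-test 0.909. If the arms differ by the same 0.71 SD but move in opposite directions (+0.355 and −0.355), pooled Friedman rejects in 3.4% of trials and the t-test in 90.7% (20,000 trials).

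The Friedman result therefore follows overall change over time, not the difference between arms.

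**The case against.** The strongest reply is that no conclusion on Hypothesis 1 need rest on this test. The Overview names ANOVA and repeated measures ANOVA as the basic tests. The change-score ANOVA, the MANCOVA contrast in TBI self-efficacy, the mixed models and the group-by-time term implied by the two-way design all compare the arms. The Friedman sentence does not name the primary CRIS subscale. This stands, and it limits the severity.

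It may also be a naming slip. Since a between-groups factor is stated, the authors may have meant a nonparametric analogue of the two-way design. That is plausible, but the test they name is not such an analogue, and an analyst following the text would run a test of time. The opening wording that methods will be considered does not help much, because the Friedman sentence itself is a commitment.

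That Friedman is also the fallback for non-normal residuals is an inference. Friedman is planned unconditionally and the fallback conditionally, so a different method may be intended. The text supports only that the fallback is unnamed and that the one nonparametric method named cannot compare arms.

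Finally, the 10% to 95% range comes from assumed shifts. Those rejections are correct detections of change over time and mislead only if read as treatment effects. The 0.71 is the CRIS planning input; the plan gives no effect size or SD for TBI self-efficacy or real-world tasks. Both limits are accepted.

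None of this makes the named test suitable for the purpose the plan gives it.

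**Conclusion.** The concern holds. As written, the plan assigns Friedman's test to a between-arm question that it cannot address. This follows from the form of the statistic and needs no assumption about the data. How far it could mislead does depend on assumptions: under equal improvement of 0.1 to 0.5 SD in both arms, a pooled test is significant in about 10% to 95% of trials, and separate tests show COMPASS alone significant in about 7% to 23%. In the other direction, it loses power against a real difference (68% against 91% at the borrowed d of 0.71). Because the test is supplementary and other planned analyses contain the arm comparison, this should be fixed but does not undermine the trial. The exposure is greatest if residuals are non-normal and Friedman is then taken as the fallback.

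**What to change.** In the SAP section for Hypothesis 1:

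- Delete the Friedman ANOVA.
- Name one between-arm nonparametric method as the fallback for non-normal residuals, for example a rank-sum test on change from baseline to post-intervention, or rank ANCOVA adjusting for baseline.
- State the trigger for that fallback.
- Use the method as a fallback or sensitivity analysis, not as a co-test sharing the Bonferroni alpha.
- State that group-by-time is the treatment test in the two-way repeated measures ANOVA.

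The cost is wording only, with no new data. The following figures use the CRIS planning d of 0.71, 44 per arm and alpha 0.05 before any Bonferroni adjustment. If change is normal, rank-sum has about 89% power against 91% for the t-test. Used only as a fallback (example trigger: Shapiro-Wilk p < 0.05 on within-arm residuals; 10,000 trials), overall power under normality stays at about 91%. Type I error is 0.050 for normal data, 0.050 for scaled t with 5 df and 0.052 for exponential data. Run instead as a co-test with alpha split to 0.025 each, it would lower the t-test's power to about 85%.

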## STATISTICAL ANALYSIS PLAN

### Overview

For this project, we plan to collect three major types of data assessed at times 1-3 (baseline/pre-intervention, 2 months/post-intervention, and 3 months follow up): community integration parameters including educational attainment and employment, individual characteristics such as PTSD; TBI self-efficacy, emotional status, coping, performance of real-world tasks, resilience and life satisfaction, and neuropsychological parameters including overall cognitive and executive functioning. Though we have removed the physical function assessments from future data collection, previously collected data on physical function may still be used for data analysis and subsequent publication and presentation purposes. The primary outcome will be the change in the three major types of parameters from pre- to post-intervention. Depending upon the hypothesis being tested (see Specific Aims section), participants will be stratified according to level of executive functioning, severity of conditions secondary to TBI (PTSD, level of functioning, emotional status), or degree of societal participation. Dependent variables will include TBI-self-efficacy, community integration indices, educational or work attainment as defined by the ICF qualifiers, and life satisfaction. Both objective (e.g. executive performance) and subjective (e.g., perceived TBI self-efficacy) data will then be obtained based on repeated measures over the three-year period. Multiple regression models will be fitted to explore continuous primary and secondary outcomes differentiating between groups at each time point and changes at the intra-individual and inter-individual levels over time. For categorical outcomes (e.g., low/high executive performance, or work status such as unemployed/employed, part-time/full-time), unconditional logistic and/or multinomial regression models will be implemented.

The basic testing of the hypotheses will involve ANOVA test and repeated measures ANOVA test. Bonferroni adjustments will be made to account for multiple testing.

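### The Hypothesis 1 repeated-measures model lists a time point as an outcome and omits the primary CRIS scale, and the self-efficacy MANCOVA has one named outcome and no adjustment for its own baseline

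*Combined protocol and SAP*

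**What the plan says.** Study Hypothesis 1 predicts that the COMPASS group will have "higher TBI self-efficacy and higher community integration scores over time". The power section is specific about the outcome: "The primary outcome of this study is the frequency of social interactions measured via the Extent of Participation subscale of the CRIS". Its null hypothesis is equal mean change in the CRIS subscale between groups from time 1 to time 2.

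The SAP Overview is broader: "The primary outcome will be the change in the three major types of parameters from pre- to post-intervention". It lists community integration indices among the dependent variables, and it says that the basic hypothesis tests are ANOVA and repeated-measures ANOVA.

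The SAP section on Hypothesis 1 offers several analyses to be considered:

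- An ANOVA of pre-to-post change between groups, with no outcome named.
- A two-way repeated-measures ANOVA and a Friedman ANOVA, "using the baseline time point, levels of TBI self-efficacy, or real-world tasks performance as the dependent variables". The time factor is then defined: "The levels of the repeated measures factor correspond to the number of assessments: baseline (pre-intervention) and 2 months post-intervention".
- A MANCOVA: "MANCOVA analysis will focus on the contrast in TBI self-efficacy between the intervention and supported discharge groups while accounting for a specified covariate". That covariate is the "level of executive impairment as defined by FrSBE".
- Linear mixed models with baseline values as a covariate, again with no outcome named.

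**The concern.** Three things do not fit together. First, baseline appears both as a dependent variable and as a level of the repeated factor in the same model, so the list cannot be run as written. Second, the section is headed for community re-integration, yet the one explicit list of outcomes omits the community-integration scale on which the trial was sized. It includes instead real-world task performance, which Study Hypothesis 2 uses as its measure of response. Third, an analysis with one named outcome is not multivariate, and this one does not adjust for the baseline value of that outcome, although self-efficacy is measured at baseline.

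An analyst who followed the text literally would never fit the repeated-measures model to the primary outcome. The choice among the remaining models would be open when the data are in hand. For self-efficacy, the MANCOVA would carry avoidable residual variance and would not correct for chance imbalance at baseline.

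**Working it through.** **The plan's own figure.** Inputs from the power section: standardised effect 0.71, SD 7, two-sided α = 0.05, power 90%, 20% loss. The noncentral t calculation gives 42.67, so 43 per group. At an effect of 0.70 it gives 43.87, so 44. With 44 per group and 0.71, power is 0.909. Then 44/0.8 = 55 per group, 110 in all. The stated sample size is reproduced and is not in question. It assumes a two-group test of CRIS change.

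**Which planned analysis reaches CRIS.**

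| Analysis in the Hypothesis 1 section | Outcome named | Own baseline used |
|---|---|---|
| Change-score ANOVA | none | yes, by subtraction |
| Repeated-measures / Friedman ANOVA | baseline time point, self-efficacy, real-world tasks | as a time level |
| MANCOVA | self-efficacy | no; FrSBe only |
| Linear mixed models | none | yes, as covariate |

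No row names CRIS. With two groups and two time points, the group-by-time test of the repeated-measures ANOVA is the same as the change-score ANOVA. Adding CRIS to the list therefore makes the intention explicit but does not create a new treatment test.

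**What own-baseline adjustment is worth for self-efficacy.** From the documents: 44 evaluable per arm and two-sided α = 0.05. Assumed, because the documents give no value: a 0.5 SD effect, equal variances at both times, baseline-to-follow-up correlation r of 0.5 to 0.7, and FrSBe-to-self-efficacy correlation f of 0.2 to 0.4. The effect in units of the relevant SD is:

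- FrSBe-only model: 0.5/√(1 − f²)
- Change score: 0.5/√(2(1 − r))
- Own-baseline ANCOVA: 0.5/√(1 − r²)

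| Model | Assumed correlation | Effect / SD | Power |
|---|---|---|---|
| FrSBe only | f = 0.2, 0.3, 0.4 | 0.510, 0.524, 0.546 | 0.66, 0.68, 0.72 |
| Change score | r = 0.5, 0.6, 0.7 | 0.500, 0.559, 0.645 | 0.64, 0.74, 0.85 |
| Own-baseline ANCOVA | r = 0.5, 0.6, 0.7 | 0.577, 0.625, 0.700 | 0.76, 0.83, 0.90 |

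The ratio of residual variances, own baseline to FrSBe only, is (1 − r²)/(1 − f²). It runs from (1 − 0.49)/(1 − 0.04) = 0.53 to (1 − 0.25)/(1 − 0.16) = 0.89. Against the change test, ANCOVA gains 0.12, 0.09 and 0.05 in power. Against the planned mixed model with baseline as covariate the gain is about nil, because the adjustment is the same.

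**The case against.** The strongest answer is that the CRIS test is specified elsewhere. The power section writes the null hypothesis as equal CRIS change, the change-score ANOVA is that test, and the Overview includes community integration indices. A reader might infer from the outcome list that CRIS is not analysed under Hypothesis 1. The documents do not support that.

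A reader might also infer that self-efficacy is tested with no protection against baseline imbalance. That is wrong too: the mixed-model bullet plans baseline adjustment, and the repeated-measures ANOVA carries baseline as a time level. The missing adjustment is specific to the MANCOVA.

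The size of the gain is also open to challenge. The contrast with 0.66 to 0.72 applies only to the FrSBe-only model. The 0.5 SD effect is not in the documents; at 0.71, the plan's effect size for CRIS, the FrSBe-only model would already have power of 0.92 to 0.95. The weak FrSBe prediction reported in the protocol concerns community integration on a different questionnaire, so it does not anchor f.

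Two smaller points also stand. The wording about the focus of the MANCOVA leaves some room for further outcomes, though none is named. And Specific Aim 1 covers everyday tasks, so their presence under Hypothesis 1 is not plainly an error.

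What the objection does not remove is that no Hypothesis 1 model names CRIS, that one listed outcome is impossible, and that nothing says which of the overlapping models decides the hypothesis. The Overview makes repeated-measures ANOVA one of the two basic tests, and that is the model whose list leaves CRIS out.

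**Conclusion.** The point holds as a fault of specification in two models, not as a gap in the whole plan. The repeated-measures list contains a time point and omits the sized primary outcome. The MANCOVA is in effect an ANCOVA of self-efficacy without its own baseline. CRIS and baseline adjustment are reachable through other planned analyses, but neither of those names CRIS and none is declared to govern.

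Under the stated assumptions, own-baseline adjustment is worth 0.05 to 0.12 in power over the planned change test, more over the FrSBe-only model, and nothing material over the planned mixed model. It should be corrected before analysis; the sample size is unaffected.

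**What to change.** In the SAP section on Hypothesis 1:

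1. Delete the baseline time point from the dependent variables.
2. Name CRIS Extent of Participation as the primary outcome, as in the power section, and TBI self-efficacy as the other Hypothesis 1 outcome. The documents do not rank self-efficacy as secondary; if a rank is wanted, the sponsor must state it.
3. Reconcile the place of real-world tasks with Hypothesis 2 and Specific Aim 1.
4. Replace the MANCOVA by an ANCOVA for each of the two outcomes, or by the mixed model already planned. Use that outcome's own baseline and baseline FrSBe as covariates, and state that this is the governing model.

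The cost is SAP wording only. The CRIS, self-efficacy and FrSBe baselines are already collected, and no further participants are needed.
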